2.7 Analytic approach

Participants demographics and clinical characteristics will first be presented. Descriptive data will be presented for each outcome measure (MARS-5, SCI, GAD-7, PHQ-9, FFS and BESS subscales) and sleep diary variables at each of the 3 timepoints (baseline, post-intervention, and 12-week follow-up).

Hypotheses will be tested using a 2x3 mixed factorial ANOVA. Between-subjects factor will be group (intervention or control), and within-subjects factor will be timepoint (baseline, post-intervention, and 12-week follow-up). We will examine the main effect of group, timepoint and interaction of group and timepoint. If a significant main effect is found, subsequent comparisons will be made applying Bonferroni correction.

3. Discussion

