2.2.1. Recruitment

We will aim to recruit a sample of 40 participants. A-priori power analysis was conducted using G*Power version 3.1.9.7 (Faul et al., 2007) to determine the minimum sample size required to test the study hypothesis using a repeated measures ANOVA (within-between interaction). Results indicated the required sample size to achieve 80% power for detecting a medium effect (significance criterion α =.05) was *N*=18. Therefore, the target sample size of *N*=40 is adequate to test the study hypothesis.

Recruitment will involve emailing participants of a previous study (UEC21/29) who indicated that they would be interested in participation in future research studies. We will contact individuals from this sample whose responses indicated they are nonadherent to their ET medication and experience significant sleep problems, informing them of the opportunity to take part in this study.

The initial email will briefly outline the nature of the study and include an information sheet with full study details. Those who are interested will be asked to respond to this initial email so that a screening interview can be scheduled.

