2.3. Procedure

Those who indicate interest in participation will be emailed a link to a virtual consent form via Qualtrics survey platform. Following informed consent, a screening interview will be scheduled. They will then be interviewed to ensure eligibility criteria are met. Screening interviews will be carried out by the PhD student: if there are any points of uncertainty, clarification will be sought through discussion with academic supervisors. Those who meet inclusion criteria following screening will be sent a link to the baseline assessment, then randomised to either the intervention or waitlist control group. All further assessments will be sent via email and carried out through Qualtrics survey platform.

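### The 2x3 mixed ANOVA treats baseline as an outcome and by default needs all three scores, so it gives up precision that a baseline-adjusted mixed model on the same data would keep

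*Combined protocol and SAP*

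**What the plan says.** Section 2.7 names a single method for the hypotheses: "Hypotheses will be tested using a 2x3 mixed factorial ANOVA". The between-subjects factor is group, and the "within-subjects factor will be timepoint (baseline, post-intervention, and 12-week follow-up"). Baseline is therefore one of three outcome levels and not a covariate. Three effects are to be looked at, with none marked as primary: "We will examine the main effect of group, timepoint and interaction of group and timepoint".

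Section 2.2.1 sizes the trial for the same family of test, "using a repeated measures ANOVA (within-between interaction"), and reports: "Results indicated the required sample size to achieve 80% power for detecting a medium effect (significance criterion α =.05) was *N*=18". It concludes: "Therefore, the target sample size of *N*=40 is adequate to test the study hypothesis". It gives no correlation between visits, no numerical effect size and no allowance for attrition.

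Section 2.4 allocates 2:1 to waitlist or intervention, which as worded is about 27 and 13 of 40. Section 2.3 places the baseline assessment before randomisation and describes the rest as remote: "All further assessments will be sent via email and carried out through Qualtrics survey platform". No section states how a missed assessment is handled, which women form the analysis set, or whether any analysis adjusts for baseline.

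**The concern.** Two features of the named method matter in a trial with about 13 treated women.

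First, baseline is measured before allocation, so the arms can differ there only by chance. Entering it as a level of time makes the group-by-time interaction as precise as an analysis of change scores. Using baseline as a covariate leaves a smaller error variance whenever the correlation between visits is below 1. The group main effect does worse, because it averages in a visit at which no effect is possible.

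Second, a conventional mixed ANOVA needs all three scores from each woman. One unanswered survey would by default remove her, together with any other follow-up score she gave. The tested set would then be completers rather than the randomised women.

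At stake are power and precision for the primary outcome, MARS-5, and for the secondary scales if they are tested in the same way.

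**Working it through.** **The plan's own figure.** Interaction test: λ = f²·N·m/(1−ρ), df = 2 and 2(N−2), with 2 groups and m = 3 visits. Assume f = 0.25 for a medium effect.
- At ρ = 0.5 and N = 18, λ = 0.0625·18·3/0.5 = 6.75 and power is 59%; 80% needs N = 28.
- At ρ = 0.69 to 0.70, N = 18 gives 81% to 82%.

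No correlation is stated, so 18 is neither confirmed nor refuted.

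**Inputs for the comparison.** From the documents: N = 40, split 13 v 27 (sections 2.2.1 and 2.4); three visits; α = 0.05. Assumed: equal correlation ρ between all visits (0.3, 0.5, 0.7), and the same effect d at both later visits (0.5 or 0.7 SD). The effective size is 13·27/40 = 8.775.

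**Like-for-like 2-df tests, complete data.**
- Planned interaction: λ = d²·8.775·2/[3(1−ρ)], df 2, 76.
- Baseline-adjusted test of both later visits: λ = d²·8.775·2/[(1−ρ)(1+2ρ)], df 2, 36.
- Ratio of the two: 3/(1+2ρ).

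Example at d = 0.7, ρ = 0.5: planned λ = 0.49·8.775·2/1.5 = 5.73; adjusted λ = 0.49·8.775·2/1.0 = 8.60.

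| ρ | Information ratio | 0.7 SD: planned v adjusted | 0.5 SD: planned v adjusted |
|---|---|---|---|
| 0.3 | 1.88 | 41% v 66% | 23% v 38% |
| 0.5 | 1.50 | 55% v 71% | 30% v 42% |
| 0.7 | 1.25 | 78% v 85% | 48% v 55% |

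The 36 denominator df are the cautious choice. With 76, the adjusted figures at 0.7 SD are 68%, 73% and 87%.

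**Like-for-like 1-df contrast, mean of the two later visits (d = 0.7, ρ = 0.5).**
- Change from baseline: variance factor (1+ρ)/2 + 1 − 2ρ = 0.75; SE = √(0.75/8.775) = 0.29 SD; power about 65% (38 df).
- Baseline-adjusted: variance factor (1+ρ)/2 − ρ² = 0.50; SE = √(0.50/8.775) = 0.24 SD; power about 81% (37 df).

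**Group main effect.** An effect pattern of 0, d, d averages to 2d/3. Simulated power at 0.8 SD with no missing data is 55%, 48% and 42% at ρ = 0.3, 0.5 and 0.7.

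**Missed surveys.** With 10%, 20% or 30% of women incomplete, 36, 32 or 28 of 40 remain under complete-case analysis. For 0.5 SD and ρ = 0.5, planned power falls from 30% to 25% at 20% incomplete. At 0.7 SD, λ falls from 5.73 to 5.73·0.8 = 4.59 (df 2, 60) and power from 55% to about 45%.

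**Bias.** One simulation was built to produce it. Treated women below their arm's week-4 median missed week 12 with probability 0.40 (others in that arm 0.05), controls with probability 0.15, and 8% missed both later visits. The ANOVA estimate was 0.74 and the mixed-model estimate 0.70, against a true 0.70. The excess of 0.04 SD is about 6% of the effect and small beside a standard error of 0.24 to 0.29 SD.

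**The case against.** Mixed ANOVA is a valid, conventional choice for a pilot that sets out to explore an effect, and it matches the test used for the sample size. That stands: baseline as a level of time does not bias the interaction test under randomisation. The cost is precision.

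The size of the loss also depends on unstated quantities. For the pattern 0, d, d, f = 0.25 means d = 0.25/√(2/36) = 1.06 SD. At that effect, with ρ near 0.7 (about what reproduces N = 18), the loss against an adjusted all-data model is only 1 to 6 points for 0% to 30% incomplete. This is fair, but 1.06 SD is a large difference between arms, and power is then near its ceiling under either method. The plan states neither that effect nor that correlation, so it cannot rely on this favourable case.

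A reader might infer that the plan orders incomplete women to be deleted. It does not. Deletion is the method's default, combined with the plan's silence; imputation is neither planned nor excluded. With no missed surveys, all 40 are analysed and nothing departs from the randomised sample.

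A reader might also set the planned 55% against the 81% available from an adjusted average of the two visits. That compares a 2-df test with a 1-df test, so part of the gap comes from changing the hypothesis. The fair pairs are 55% v 71% and 65% v 81%.

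**Conclusion.** The concern holds in a bounded form. The plan's only named analysis enters baseline as an outcome, by default needs complete cases, and is accompanied by no missing-data rule or analysis set. With complete data and 13 v 27 women, the like-for-like 2-df loss is about 7 to 25 points of power at 0.7 SD and 7 to 15 points at 0.5 SD, over correlations of 0.7 down to 0.3. Missed surveys would add to it.

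The documents do not support saying that most of the power is wasted whatever the circumstances, that the interaction test is biased, or that completers-only analysis would seriously overstate the effect. Any such bias looks modest even in an unfavourable scenario. All these sizes rest on assumed correlation, effect and attrition, equal correlation between visits and an equal effect at both follow-ups. The direction of the precision loss does not depend on the particular values: 3/(1+2ρ) exceeds 1 for any ρ below 1.

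**What to change.** In section 2.7, replace the ANOVA with a linear mixed model for MARS-5 at post-intervention and 12 weeks. Use group, visit and group-by-visit as fixed effects, baseline MARS-5 as a covariate, an unstructured or compound-symmetry covariance, and small-sample degrees of freedom. Include every randomised woman with at least one follow-up score, as allocated, and report how many have none.

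Name one primary contrast in advance, for example the group difference averaged over the two visits. Without a named contrast, the power figures belong to no particular test. Use the same model for the secondary scales, and make the power statement in section 2.2.1 describe the chosen contrast with its correlation, effect size and attrition stated.

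The cost is SAP wording and slightly more analysis work, with no new data. The model relies on data being missing at random, a weaker assumption than a completers-only ANOVA needs.

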One side effect which may present an appropriate target is insomnia. Characterised by difficulty falling and staying asleep, insomnia common in cancer patients and especially among those diagnosed with BC(9). This is debilitating to carrying out daily activities and has further effects on mental health and ability to move on from BC treatment(8). Importantly, sleep problems are influenced by other treatment side effects such as hot flashes, night sweats, and musculoskeletal pain, and related to depression and anxiety in BC survivors(10,11). Insomnia is therefore a transdiagnostic symptom with the potential to

reduce the burden of several different ET side effects and overall quality of life. Unlike hot flashes and pain, sleep can be treated non-pharmacologically using cognitive behavioural therapy, which is considered the gold standard treatment for insomnia (12). This has been found to improve not only insomnia symptoms but also depression, anxiety, and fatigue in BC survivors(13), and can be delivered efficiently to groups of people and treat these symptoms non-pharmacologically(14,15).

Thus far, interventions to improve ET adherence have focused on patient education and reminders to take medication, which have had little success in improving adherence (Ekinci et al., 2018; Heiney et al., 2019). Recent protocols include components of side effect management(16), which addresses research finding that BC survivors express a desire for support and willingness to try new strategies with the aim of better side effect management (7,8). However, to the best of our knowledge, there have been no attempts to improve adherence by targeting a specific ET side effect. Sleep may present an opportunity here as it is a transdiagnostic target which is highly prevalent in this population, and can be effectively treated non-pharmacologically using CBT-I.

This study will utilise a randomised, waitlist-controlled design. We will aim to recruit 40 BC survivors who experience sleep problems and struggle to take their ET medication as prescribed. The main objective of this study is to explore the effect of CBT-I (delivered through videoconferencing) on sleep problems and adherence to ET in BC survivors.

2. Methods

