2.4. Randomisation

Participants will be allocated on a 2:1 basis to the waitlist or intervention group. The study team will have no influence over the randomisation process. Participants will be randomised using block randomisation in blocks of 10. The advantage of this method is that it maintains balance between intervention and control group, as significant imbalance would reduce the power of the study in a small sample (Lim & In, 2019; Pinto et al., 2022).

Upon providing informed consent, participants will be assigned a unique identifier (UID). A PhD student unrelated to the study will be given a list of these UIDs and use an online randomisation tool to generate an allocation sequence, which will be used to assign each group's participants. They will then pass the list of UIDs assigned to each group to the PhD student for the study, who will establish which participants are in each group. Following randomisation, the intervention group will be emailed a recurring link to access CBT-I sessions via videoconferencing.

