2.5. Intervention

CBT-I is a multi-component, evidence-based intervention which incorporates both cognitive and behavioural techniques to address symptoms of insomnia, aiming to improve satisfaction with the duration and quality of sleep by reducing trouble falling and/or staying asleep. Its main components include: sleep restriction, stimulus control, and cognitive restructuring. Sleep restriction aims to reduce discrepancy between time spent in bed and time actually sleeping by improving 'sleep efficiency' (SE), which is the time spent sleeping expressed as a percentage of time spent in bed. The individual is given a prescribed bedtime and waketime to match their time spent in bed with time sleeping, which is adjusted accordingly when their SE reaches 90%, or falls below 85%. Stimulus control involves strengthening the association between being in bed and being asleep, by minimising activity in the bed unrelated to sleep or intimacy, getting out of bed if unable to initiate sleep or get back to sleep after waking up, and only returning to bed when sleepy. Cognitive restructuring challenges maladaptive beliefs about sleep and concerns about the daytime consequences of poor sleep, to reduce arousal and anxiety associated with insomnia.

CBT-I will be delivered over 4 weekly 1-hour sessions, via videoconferencing. Session 1 will include psychoeducation about sleep (the relationship between sleep and mental health, the '3P' model of insomnia), and begin to explain components of CBT-I (sleep restriction and relaxation). Session 2 will reinforce previous learning about these components and introduce stimulus control. Session 3 will introduce sleep hygiene and its importance in preventing poor sleep. Session will 4 discuss cognitive therapy techniques and relapse prevention.

Participants in the waitlist condition will receive the CBT-I intervention after completing the 12-week follow-up assessment. This will then be used as a baseline measure for these participants to compare to their post-intervention and follow-up after receiving the treatment.

The intervention will be delivered by a PhD student, who will receive extensive CBT-I training from supervisors who have over 15 years' experience in delivering CBT-I. The student will receive continuous supervision throughout. Sessions will be recorded and 10% will be assessed by supervisors to monitor treatment fidelity.

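### The plan ties its hypothesis to the group-by-time interaction but makes a significant main effect the stated trigger for follow-up comparisons; how often this matters depends on the effect size

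*Combined protocol and SAP*

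**What the plan says.** Section 2.2.1 (Recruitment) sizes the trial "to test the study hypothesis using a repeated measures ANOVA (within-between interaction"), with "80% power for detecting a medium effect" at two-group alpha 0.05. The interaction is therefore the test that carries the hypothesis.

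Section 2.7 (Analytic approach) specifies a mixed ANOVA with two groups and three timepoints. It lists the effects separately: "We will examine the main effect of group, timepoint and interaction of group and timepoint". The next sentence is the only follow-up rule: "If a significant main effect is found, subsequent comparisons will be made applying Bonferroni correction". The comparisons that make up the Bonferroni family are not named.

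Three other places bear on this:
- Section 2.5: "Participants in the waitlist condition will receive the CBT-I intervention after completing the 12-week follow-up assessment". The waitlist arm is therefore untreated at all three analysed timepoints.
- The Introduction gives the objective as to "explore the effect of CBT-I (delivered through videoconferencing) on sleep problems and adherence to ET in BC survivors". The follow-up rule thus matters for the sleep outcomes as well as for MARS-5.
- Section 2.7 also plans descriptive summaries ("Descriptive data will be presented for each outcome measure (MARS-5, SCI, GAD-7, PHQ-9, FFS and BESS subscales") at each timepoint, but does not say they will be shown by arm.

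**The concern.** An interaction F test with 2 degrees of freedom says that the arms changed differently. It does not say which arm did better, by how much, or whether the difference lasts to 12 weeks. The follow-up comparisons should answer those questions, yet their stated trigger is a different effect.

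Two things can go wrong on the text as written. A significant interaction without a significant main effect has no planned comparison to interpret it. And a change common to both arms, such as a general drift in sleep or adherence scores, can open comparisons that are not about CBT-I. Because the comparisons are unnamed, the analyst would also choose them after seeing the data.

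**Working it through.** **Inputs from the protocol.** N = 40 and alpha 0.05 (2.2.1); three timepoints (2.7); allocation (2.4) "Participants will be allocated on a 2:1 basis to the waitlist or intervention group", taken as 27 waitlist and 13 CBT-I. Section 3.1 expects little improvement in insomnia without treatment, which supports a flat waitlist arm for sleep.

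**Assumed, because the documents give no figure.** SD 1; equal correlation between visits of 0.5 (range 0.3 to 0.7); the same effect of d SD at both follow-ups; f = 0.25 for a medium effect; no dropout; independent participants, although section 3.1 has CBT-I delivered in groups of about 5.

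**1. What each effect measures.** Take expected means of (0, d, d) for CBT-I and (0, 0, 0) for waitlist.
- Group main effect: (0 + d + d)/3 = 2d/3. With randomised arms this is caused by allocation to CBT-I; it is diluted to two-thirds by the pre-treatment baseline, but not confounded.
- Time main effect: the average change over treated and untreated arms. If both arms change by s, it is s even when CBT-I does nothing.
- Interaction: d at each follow-up, and zero when the change is shared.

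**2. The plan's own figure.** Noncentral F with lambda = f² × N × 3/(1 − rho) and df 2 and 2(N − 2).
- rho = 0.5: N = 28 gives lambda = 0.0625 × 28 × 3/0.5 = 10.5 and 81% power. N = 18 gives 59%.
- rho = 0.7: N = 18 gives lambda = 0.0625 × 18 × 3/0.3 = 11.25 and reaches 80%.

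The stated N = 18 is thus attainable at a correlation of about 0.7, an input the protocol does not give.

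**3. Translating f into SD units.** f² = p(1 − p) × (2/9) × d². With p = 13/40, f² = 0.2194 × 0.2222 × d², so f = 0.221d and f = 0.25 means d = 1.13. With equal arms it is 1.06. Effects of 0.5 and 0.8 SD correspond to f of about 0.11 and 0.18.

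**4. How often the two rules part.** Simulated 2×3 mixed ANOVA, 13:27, unweighted time means, correlation 0.5. The main-effect trigger is met if the group or the time F test is significant.

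| d (SD) | Interaction significant | Main-effect trigger met | Share of significant interactions with no main effect (correlation 0.3 to 0.7) | Same, as share of all trials |
|---|---|---|---|---|
| 0.5 | 30% | 45% | 43% (33% to 46%) | 13% |
| 0.8 | 67% | 82% | 14% (6% to 17%) | 9% |
| 1.13 | 93% | 98% | 1.4% (0.1% to 2.2%) | 1.3% |

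The shares for the three effects rise to 64%, 33% and 8.5% if time means are weighted by arm size (the plan names no sums-of-squares type), and to 50%, 22% and 4% if the effect is present at one follow-up only.

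**5. The trigger when CBT-I does nothing.** With no effect of any kind, two tests at 0.05 open comparisons in about 1 − 0.95² = 0.0975, or 10%, of trials. With a shared change of 0.1 to 0.3 SD the figure is 13% to 45% at correlation 0.5, and 12% to 66% over correlations 0.3 to 0.7. The interaction is significant in 5% throughout.

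**6. Precision of a between-group difference at one follow-up, correlation 0.5.** The standard error factor is √(1/13 + 1/27) = 0.338.
- Change score: variance 2(1 − 0.5) = 1, so the 95% CI half-width is 2.02 × 0.338 = 0.68 SD.
- Baseline-adjusted: variance 1 − 0.5² = 0.75, so the half-width is 2.03 × 0.338 × √0.75 = 0.59 SD.
- Each Bonferroni-corrected change comparison (alpha 0.025) has about 21%, 52% and 84% power at 0.5, 0.8 and 1.13 SD.

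**The case against.** **The sentence does not say 'only if'.** This is correct. The interaction is among the effects to be examined, and silence on following it up is not a bar. A reader might infer that the plan leaves its hypothesis untested or forbids follow-up; the text supports neither. 'Main effect' may also have been meant loosely, as any significant omnibus result. But the preceding sentence separates main effects from the interaction, so the loose meaning would need to be stated, and the comparisons would still be unnamed.

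**The group main effect is a legitimate signal.** Also correct. A reader might infer that neither main effect can reflect CBT-I. Under randomisation, with the waitlist untreated to week 12, that fails for group, which is diluted and not confounded. The criticism of mixing in shared change applies to time alone.

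**The consequence is small at the planning effect.** If medium means f = 0.25, the share is about 1.4%, and 0.1% at the correlation of 0.7 that reproduces N = 18. The 43% belongs to an effect less than half that size. This stands, but a pilot exploring an indirect effect of sleep treatment on adherence cannot count on 1.13 SD.

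**An interaction trigger has a price.** With a real effect, the present trigger is met more often: 45% against 30% at 0.5 SD, and 82% against 67% at 0.8 SD. Two planned, Bonferroni-corrected contrasts would not strictly need an omnibus test first. Both points stand. They are the reason to report estimates with intervals whatever the test result.

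**Conclusion.** The point holds as a gap in the written rule. The hypothesis sits on the interaction, the stated trigger is a main effect, no rule covers a significant interaction, and the comparisons are not named. That much rests on the text alone.

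The practical size is conditional. It is negligible near f = 0.25, moderate at 0.8 SD and substantial at 0.5 SD, under assumed SD, correlation, effect shape, allocation and independence within therapy groups. In the other direction, comparisons opened under a shared change are a mixture. Some reflect a real time effect, but at a shared change of 0.1 SD most occur at the roughly 10% chance rate. They should be called neither all errors nor all correct detections.

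A reader might also infer that N = 18 is wrong. The documents do not show that; it depends on an unstated correlation, and this point does not rely on it. Severity: minor to moderate.

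**What to change.** Replace the last sentence of section 2.7 with:

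> For each outcome the test of CBT-I is the group-by-time interaction, with MARS-5 primary. If it is significant, the groups will be compared on change from baseline at post-intervention and at 12 weeks, Bonferroni-corrected for two comparisons. Main effects will be reported but will not trigger comparisons; a time effect will not be read as a CBT-I effect. Whatever the test result, the between-group difference at each follow-up, adjusted for the baseline score, will be reported with a 95% CI as the main estimate.

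State that the descriptive tables will be shown by arm.

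The interaction F test is the same under weighted and unweighted time means, so this rule does not depend on the sums-of-squares type. The cost is a few sentences, by-arm tables and one baseline-adjusted model using scores already collected; no extra participants or assessments are needed. The statistical cost is that corrected comparisons open somewhat less often when CBT-I works, which the unconditional intervals largely offset.

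A separate point to reconcile: section 2.6.2 schedules sleep diaries at baseline and during the 4-week intervention period, while section 2.7 lists diary variables at the 12-week follow-up as well.

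### Section 2.7: Holm's correction in place of Bonferroni would gain about 3–4 points of power per real follow-up contrast at the same familywise error

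*Combined protocol and SAP*

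**What the plan says.** Section 2.7 plans a 2x3 mixed ANOVA with group (two levels) and timepoint (baseline, post-intervention, 12-week follow-up). It states: "We will examine the main effect of group, timepoint and interaction of group and timepoint". The follow-up rule is one sentence: "If a significant main effect is found, subsequent comparisons will be made applying Bonferroni correction".

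The section does not list the comparisons or say how many there are. It mentions neither a step-down nor a closed procedure, and it gives no sphericity correction. The trigger names a main effect. No follow-up rule is written for the interaction, although the interaction is the treatment effect over time.

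On size, 2.2.1 says: "We will aim to recruit a sample of 40 participants". Section 2.4 says: "Participants will be allocated on a 2:1 basis to the waitlist or intervention group". That gives about 13 intervention and 27 waitlist participants.

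**The concern.** The comparisons pass two hurdles: a significant omnibus F, then a Bonferroni threshold. With three timepoints there are three pairwise contrasts, so each is judged at 0.05/3 = 1.67%. Bonferroni is never better than Holm for familywise error control, because Holm applies the Bonferroni threshold only to the smallest p-value and relaxes it for the rest.

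At stake is how well the trial can say when a change appeared and whether it lasted to 12 weeks. With about 13 treated women these contrasts have limited power, and some of it is given up for no return in error control.

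**Working it through.** **The plan's own figure.** The only power figure is N=18 in 2.2.1, for the omnibus within-between interaction. With f = 0.25 (my reading of a medium effect), two groups, three visits and sphericity, λ = f²·N·3/(1−ρ) on 2 and 2(N−2) df.

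- ρ = 0.5: λ = 0.0625 × 18 × 3 / 0.5 = 6.75 on 2 and 32 df. Power is 59.5%, and N=28 would be needed.
- ρ = 0.7: λ = 3.375 / 0.3 = 11.25. Power is 82.5%, and N=18 is the result.

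The plan states no ρ, so N=18 cannot be called wrong. It does not concern the follow-up comparisons, and their correction does not alter it.

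**Inputs for the follow-up comparisons.** From the documents: three timepoints, N=40, 2:1 allocation, α = 0.05. Assumed: a family of three pairwise contrasts, two-sided tests, equal variances, compound symmetry with ρ = 0.5, no dropout, and an arm difference that is the same post-intervention and at 12 weeks. Two contrasts (baseline to post, baseline to 12 weeks) are then real, and the third (post to 12 weeks) is null. Effects are in SD of change, σ√(2(1−ρ)), which equals σ at ρ = 0.5.

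**Thresholds.** The standard error of an arm difference in change is √(1/13 + 1/27) = 0.338 SD. Holm compares the ordered p-values with 0.05/3, 0.05/2 and 0.05 and stops at the first failure. With 38 df:

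| Level | t | Difference needed |
|---|---|---|
| 0.0167 (Bonferroni for all three; Holm step 1) | 2.505 | 0.338 × 2.505 = 0.85 SD |
| 0.025 (Holm step 2) | 2.334 | 0.338 × 2.334 = 0.79 SD |
| 0.05 (Holm step 3; closed test) | 2.024 | 0.338 × 2.024 = 0.68 SD |

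**Simulated power.** The gate is the interaction F on 2 and 76 df, followed by t-tests on change scores. There were at least 40,000 trials per setting. The closed test takes each contrast at 5% once the gate is passed.

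| Effect | Quantity | Bonferroni | Holm | Closed |
|---|---|---|---|---|
| 0.8 SD (gate 67%) | each real contrast | 45% | 48% | 57% |
| | both real contrasts | 29% | 35% | 47% |
| | at least one contrast | 61% | 61% | 66–67% |
| 1.0 SD (gate 86%) | each real contrast | 67% | 71% | 79% |
| | both real contrasts | 52–53% | 59–60% | 71% |
| none | familywise error | 3.7% | 3.7% | 5.0% |

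Ranges show differences between runs. Holm cannot raise the chance of at least one rejection, because its first step is the Bonferroni step.

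**The literal trigger.** The table follows up the interaction, whereas 2.7 names a main effect. For the timepoint main effect, at a sustained 0.4 SD shift, the pattern is the same: 51%, 54% and 63% per contrast.

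**Where the loss arises.** The gate itself costs at most about 0.6 points. Nearly all the loss comes from the Bonferroni step.

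**The closed test without sphericity.** I used two illustrative covariance patterns under the complete null: correlations 0.7, 0.3, 0.6 with equal SDs; and a halved baseline SD with correlations 0.4, 0.3, 0.8. With the uncorrected F, familywise error was 5.7–6.0% for the closed test and 3.1–3.3% for gated Bonferroni.

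**The case against.** **The rule is valid and conventional, and this is a pilot.** That stands. The loss is one of efficiency. A reader might infer that the planned analysis is in error or that the interaction test loses power; neither follows.

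**A larger gain is tempting.** Among three pairwise contrasts, if any two are null so is the third. Once the omnibus null is rejected, each contrast can therefore be tested at 5%. From this a reader might infer that 2.7 throws away 18 points of power and that Holm or a closed test would restore them. The documents do not support that, for three reasons:

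- Eighteen points is roughly the ceiling for the closed test, seen above for showing both contrasts (47 − 29). The closed-test gain per contrast is about 12 points. Holm's is 3–4.
- The closed shortcut needs a valid omnibus F, and 2.7 plans no sphericity correction. Bonferroni or Holm on separately estimated contrasts does not need sphericity.
- The shortcut holds only for the three pairwise contrasts of one effect. For arm comparisons at each visit, it gave 8.4–9.7% familywise error when only one visit differed.

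**Strictness offsets the many outcomes.** Section 2.7 examines three ANOVA effects for many outcomes, with no adjustment across them stated. That is a fair reason not to loosen familywise control within a family. It is no reason to prefer Bonferroni to Holm, since both hold the same limit.

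**The trigger is a main effect.** Read literally, only timepoint needs follow-up, since group has two levels. Contrasts pooled over arms do not show a treatment effect. This stands, and the fix therefore names both effects.

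**A baseline comparison.** A reader might also infer that part of the 5% is spent comparing arms at baseline. Section 2.7 plans no such comparison.

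**Conclusion.** The point holds as a cheap improvement. In the modelled setting Holm gains about 3–4 points per real contrast and 6–7 points for showing both. It adds nothing to the chance of finding at least one, and familywise error stays within the same limit.

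That Holm never rejects less than Bonferroni is certain. The size of the gain rests on a family of three, 13 against 27, compound symmetry at 0.5, and a sustained 0.8–1.0 SD effect. The plan gives neither the family nor the correlation. The 5% limit applies to one effect for one outcome.

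**What to change.** In 2.7, put Holm's step-down correction in place of the Bonferroni correction. State that it applies to follow-up of the timepoint effect and of the group-by-timepoint interaction. This changes one sentence and needs no new data.

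The cost is that Holm gives no matching simultaneous intervals. Report ordinary 95% intervals, or Bonferroni-width ones, beside the adjusted p-values.

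Optional: for the three pairwise timepoint contrasts of a single effect only, use the closed test, each at 5% after a significant omnibus test of that effect. Adopt it only with a sphericity correction to the omnibus F, such as Greenhouse-Geisser. Any other set of comparisons stays with Holm.
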